5. AMENDMENTS AND UPDATES

Amendment or Update Number	Date	Section of Study Protocol	Amendment or Update	Reason
1	14 April 2016	various	Amendment	Adding 300 subjects treated with F/TAF and 300 subjects treated with R/F/TAF, adding blood pressure, CD4 nadir, adding historic creatinine and urine parameters, allowing full 24 months documentation even if subjects switch therapies, adding cardiovascular and renal risk factors, changes to Medical Monitor, updated study timelines
2	12 April 2019	various	Amendment	Addition of product references, update of MAH, update of EU QPPV contact details, update of definitions of special situations

- **Protocol Modifications**

Protocol modifications may only be made by Gilead. Approval must be obtained before changes can be implemented.

6. MILESTONES

Milestone	Planned Date
Start of data collection	4 th Jan 2016
End of data collection	4th quarter 2019
Registration in the EU PAS register	5 th Oct 2015
Final report of study results	3rd quarter 2020

7. RATIONALE AND BACKGROUND

7.1. Rationale for the Current Study

HIV-1 infection remains a life-threatening and serious disease of major public health significance. There are now approximately 35 million people infected worldwide {27071}. Globally, incidence continues to grow, with 2.2 million people newly infected with HIV-1 in 2011 alone. The prevalence of people living with HIV-1 infection is also increasing. Patients are being diagnosed earlier, and are living longer due to the success of highly active antiretroviral (ARV) therapy (ART).

Morbidity and mortality for HIV-1 infected patients is increasingly driven by non-AIDS associated comorbidities such as kidney, liver, and heart disease {19947}, {19948}, {22552}. Even with ART, patients with HIV-1 infection experience more age-related comorbidities, such as renal and bone disease, which manifest earlier than their age-matched HIV-uninfected peers {19946}. Moreover, the prevalence and incidence of chronic kidney disease (CKD) and end-stage renal disease (ESRD) is expected to rise as the prevalence of HIV-1 infection continues to rise {22553}.

Current treatment guidelines recommend that patients initiate therapy earlier, thereby requiring lifelong treatment, potentially for 50 years or more {19967}. Accordingly, there is a need for new HIV therapies that improve on the current standard of care so that lifelong ART is more effective, more tolerable, and safer for patients.

Tenofovir (TFV) is a nucleotide analog that inhibits HIV-1 reverse transcription. While tenofovir disoproxil fumarate (TDF), an oral prodrug of TFV, is a preferred NRTI for initial therapy, nephrotoxicity is an identified risk, and reductions in bone mineral density (BMD) have been shown that are larger than those seen with other NRTIs. Tenofovir alafenamide (TAF) is also an oral prodrug of TFV. TAF is more stable in plasma than TDF, provides higher intracellular levels of the active phosphorylated metabolite tenofovir diphosphate (TFV DP), and results in approximately 90% lower circulating levels of TFV relative to TDF at the clinical doses. These characteristics of TAF are associated with effective suppression of viral replication, and an improved tolerability and safety profile of TAF compared to TDF.

Gilead has coformulated TAF with the HIV-1 INSTI elvitegravir (EVG; E), the pharmacoenhancer cobicistat (COBI; C), and the NRTI emtricitabine (FTC; F) into an FDC tablet that is suitable for once-daily use. Thus E/C/F/TAF FDC provides a potent, convenient, tolerable, and practical regimen for the long-term treatment of patients with HIV-1 infection. Findings from two randomized, double-blind, Phase 3 trials of TAF versus TDF, both coformulated with elvitegravir, cobicistat, and emtricitabine, demonstrated non-inferior efficacy of TAF versus TDF, with a significantly improved effect of TAF compared to TDF on eGFR, proteinuria, albuminuria, and bone mineral density {34827}.

Furthermore Gilead has coformulated TAF with the NRTI emtricitabine (FTC; F) into a fixed dose combination (FDC) tablet for once daily use (in combination with other ARV agents) and

coformulated TAF with the HIV-1 non-nucleoside reverse transcriptase inhibitor (NNRTI) rilpivirine (RPV; R) and the NRTI emtricitabine (FTC; F) into a fixed dose combination (FDC) tablet for once daily use.

In this non-interventional observational German study we are aiming to describe effectiveness and safety of Elvitegravir/Cobicistat/Emtricitabine/Tenofovir alafenamide (E/C/F/TAF) or Emtricitabine/Tenofovir alafenamide (F/TAF) or Rilpivirine/Emtricitabine/Tenofovir alafenamide (R/F/TAF) in treatment-naïve and treatment-experienced HIV-1 infected adult patients as well as adherence, resource utilization, patient reported outcome data about quality of life, health status and treatment satisfaction of E/C/F/TAF, F/TAF or R/F/TAF treated patients during daily routine use.

8. RESEARCH QUESTIONS AND OBJECTIVES

To describe effectiveness, safety, adherence, resource utilization, and patient reported outcomes of E/C/F/TAF, F/TAF or R/F/TAF use in routine care.

The primary objective of this study is as follows:

- To evaluate HIV-1 RNA and CD4 cell count changes for patients using E/C/F/TAF, F/TAF or R/F/TAF within a time period of 24 months

The secondary objectives of this study are as follows:

- To describe rates of ADRs/SADRs for E/C/F/TAF, F/TAF and R/F/TAF
- To describe the motivation for ART initiation in treatment-naïve subjects (eg, early treatment according to guidelines, treatment as prevention, patient wish) and factors driving the ART switch to E/C/F/TAF, F/T/AF or R/F/TAF in treatment-experienced subjects (eg, simplification of ART, patient preference, side effects of current ART)
- To describe adherence (number of missed E/C/F/TAF, F/T/AF or R/F/TAF doses) and reasons for E/C/F/TAF, F/TAF or R/F/TAF discontinuation during the study
- To describe physical and mental health-related quality of life, health status, and treatment satisfaction using standardized questionnaires (Health Survey Short Form (SF-36), HIV Symptom Index, and HIV Treatment Satisfaction Questionnaire (only for treatment-experienced subjects))
- To describe health care resource utilization (eg, number of hospitalizations, number of physician visits)

The above parameters will be evaluated separately per treatment arm and in various subgroups (eg, treatment-naïve subjects versus treatment-experienced subjects, age (< 50 years, ≥ 50 years), presence of specific comorbidities, sex).

The collection of ADR/SADR reflects the real-life situation, in which the treating physician with best knowledge of his patient assesses whether an observed event could be related to a given treatment. In this way, the study will collect safety data that is reflective of the real-life setting in which it is conducted.

9. RESEARCH METHODS

9.1. Study Design

This non-interventional study does not influence the treatment decisions made by the participating physicians. Subjects can be enrolled in this study after the physician has decided to treat a specific subject with E/C/F/TAF, F/TAF or R/F/TAF in accordance with the approved respective SmPCs. All treatments will be prescribed according to local treatment guidelines and/or routine clinical practice. The treating physician will make all treatment decisions and will provide prescriptions for his/her patients. There will be no study-specific procedures.

The study is designed as a multicenter, non-interventional observational cohort study, in accordance with the German Drug Act (§63f AMG). It is planned to enrol a total of 900 adult (age ≥ 18) HIV-1 infected subjects initiating treatment with E/C/F/TAF (n=300), F/TAF (n=300) or R/F/TAF (n=300) in routine care. The study will enroll approximately 150 treatment-naïve and 150 treatment-experienced subjects in each arm.

Data collection will be performed by manual entry of data from the patient's medical file and questionnaires to a computer-based electronic case report form (eCRF). No patient initials will be included.

Data will be prospectively collected for each enrolled subject for approximately 24 months. In case of E/C/F/TAF, F/TAF or R/F/TAF discontinuation the date of discontinuation, reasons for discontinuation (eg, patient wish, adverse reaction, insufficient efficacy) and subject's new ART will be collected. The subject will remain in the study and will be continuously documented with the new ART until premature end of documentation (eg, due to lost to follow up) or until reaching the defined end of documentation approximately 24 month after enrollment.

9.2. Setting

9.2.1. Study Time Period

Data will be documented at the following time points:

Baseline (start of E/C/F/TAF, F/TAF or R/F/TAF therapy) – at baseline the historic data on serum creatinine, quantitative urine parameters and body weight will be documented.

Follow-up: approximately 3 months, 6 months, 12 months, 18 months, and 24 months after E/C/F/TAF, F/TAF or R/F/TAF therapy initiation (baseline) according to clinical practice.

9.2.2. Population

The study will enroll approximately 900 adult (age ≥ 18) treatment-naïve and treatment-experienced HIV-1 infected subjects initiating treatment with E/C/F/TAF, F/TAF or R/F/TAF (300 subjects per arm) in accordance with the respective SmPC in routine care.

To evenly represent treatment-naïve and treatment-experienced patients the study will enroll in each arm approximately 150 treatment-naïve and 150 treatment-experienced subjects.

The total study size of 300 subjects per arm has been chosen to allow the evaluation of collected parameters also within several subgroups per arm (eg, treatment-naïve subjects versus treatment-experienced subjects, age (< 50 years, ≥ 50 years), presence of specific comorbidities, sex), assuming that such subgroups are represented in substantial numbers. Details of subgroup definition will be documented in the Statistical Analysis Plan.

Participating study sites (hospitals and private practitioners) are specialized on treating HIV patients. All study sites are located in Germany.

9.2.3. Inclusion Criteria

Subjects must meet *all* of the following inclusion criteria to be eligible for documentation in this study:

9.2.3.1. Arm 1 (E/C/F/TAF)

- HIV-1 infection
- Signed informed consent
- ≥ 18 years old
- Initiating treatment with E/C/F/TAF in accordance with the E/C/F/TAF SmPC

9.2.3.2. Arm 2 (F/TAF)

- HIV-1 infection
- Signed informed consent
- treatment-naïve subjects ≥ 18 years old
- treatment-experienced subjects ≥ 50 years old
- Initiating treatment with F/TAF (in combination with other ARV medication) in accordance with the F/TAF SmPC

9.2.3.3. Arm 3 (R/F/TAF)

- HIV-1 infection
- Signed informed consent
- ≥ 18 years old
- Initiating treatment with R/F/TAF in accordance with the R/F/TAF SmPC

9.3. Variables

Prior to E/C/F/TAF, F/TAF or R/F/TAF therapy initiation (baseline):

Gender, year of birth, body weight and height

Race

Date of HIV-1 diagnosis

CDC stage

Co-morbidities as available from medical records (eg, cardiovascular diseases, asthma, COPD, hypertension, hyperlipidemia, neuropsychiatric disorders, osteopathic disorder, diabetes mellitus, nephropathy, chronic hepatitis B, chronic hepatitis C)

Laboratory parameters as available from medical records:

- HIV-1 RNA and limit of detection of the used assay
- CD4 cell count
- AST, ALT, gamma-GT
- Albumin
- Urine albumin/creatinine ratio (UACR), urine protein/creatinine ratio (UPCR)
- Serum total protein
- Triglycerides
- Total cholesterol

- HDL, LDL
- Serum glucose
- Serum phosphate
- Serum creatinine
- Serum uric acid
- Blood urea nitrogen (BUN)
- Calcium, chloride, magnesium, potassium, sodium
- Urine dipstick parameters (glucose, leukocytes, nitrite, protein, pH, ketone bodies)
- Urine quantitative protein, albumin, and creatinine
- Hematology profile (complete blood count with differential and platelet count)
- Bone mineral density

History of anti-retroviral therapy

CD4 nadir

Blood pressure

Historic serum creatinine, quantitative urine creatinine, quantitative urine albumin, quantitative urine protein, and body weight within the last 2 years prior to E/C/F/TAF, F/TAF or R/F/TAF treatment initiation

Co-medications as available from medical records

Resistance status as available from medical records

Motivation for ART initiation in treatment-naïve subjects (eg, early treatment according to guidelines, treatment as prevention, patient wish) and factors driving the ART switch to E/C/F/TAF, F/TAF, or R/F/TAF in treatment-experienced subjects (eg, simplification of ART, patient preference, side effects of current ART)

Cardiovascular and renal risk factors (family history of angina/heart attack, smoking status, intravenous drug use, prior use of atazanvir, tenofovir disoproxil fumarate (TDF), indinavir or lopinavir)

HIV Symptom Index

HIV Treatment Satisfaction Questionnaire (only for treatment-experienced subjects)

SF-36

During follow-up (approximately 3 months, 6 months, 12 months, 18 months, and 24 months after starting E/C/F/TAF, F/TAF, or R/F/TAF therapy):

Anti-retroviral therapy adherence (VAS scale and number of missed doses during the last 4 and 30 days). The questionnaire with the VAS scale and the questions about the missed doses will be handed to the patients, filled in by the patients and the patient will put the questionnaire into an envelope. Only the closed envelope will be returned to the site staff. The closed envelope which only contains the subject number as identifier will be sent by the site to the CRO for data entry. The site will not know any information the patient entered into the questionnaire.

In case of E/C/F/TAF, F/TAF or R/F/TAF discontinuation: date of discontinuation, reasons for discontinuation (eg, patient wish, adverse reaction, insufficient efficacy) and subject's new ART. The subject will remain in the study and will be continuously documented with the new ART until premature end of documentation (eg, due to lost to follow up) or until reaching the defined end of documentation approximately 24 month after enrollment.

Changes in co-medications as available from medical records

Laboratory parameters: see baseline

New AIDS-defining events (CDC class C, excluding CD4 cell count < 200 cells/ μ L)

Changes in co-morbidities/co-infections

ADRs and SADR for all ARV drugs used in the study

Special situations reports as appropriate

Only approximately 12 months and 24 months after starting E/C/F/TAF, F/TAF, or R/F/TAF therapy: Blood pressure and cardiovascular and renal risk factors (eg, family history of angina/heart attack, smoking status, intravenous drug use)

HIV Symptom Index

HIV Treatment Satisfaction Questionnaire (only for treatment experienced subjects and only approximately 3 months, 6 months and 12 months after E/C/F/TAF, F/TAF or R/F/TAF therapy initiation)

SF-36

In case of virologic failure: resistance status as available

Resource Utilization (number and duration of hospitalizations, number of appointments with HIV-treating physician and with other physician types between the documented visits)

9.4. Health Care Resource Utilization Data Sources

Subjects will receive a questionnaire on which they will be asked to document any hospitalizations (number and durations) and number of appointments with other physician types (eg, renal or bone specialists).

The site will document the number of visits of the subject at the site between the visits documented in the eCRF.

9.5. Study Size

Previous studies showed percentages of viral suppression (< 50 copies/mL):

Treatment	after 48 weeks	after 96 weeks
E/C/F/TAF	92% treatment-naïve {34827}	87% treatment-naïve {39846}
	97% treatment-experienced {38028}	not available yet
F/TAF	94% treatment-experienced {39786}	not available yet
R/F/TAF	90% treatment-naïve* {20441}	84% treatment-naïve* {20441}

* these data are estimates for R/F/TAF based on data for Eviplera (rilpivirine/emtricitabine/tenofovir disoproxil fumarate): viral suppression rates for treatment-naïve patients with baseline viral load of $\leq 100,000$ copies/mL after 48 (89.6%) and 96 weeks (83.7%) as R/F/TAF data are not available yet

Due to missing data rates after 96 weeks compared to 48 seem to be decreasing with less pronounced differences between treatment-naïve and treatment-experienced patients.

A sample size of 300 subjects per arm will provide 80% power to detect a difference in the treatment-naïve and treatment-experienced group means when the expected effect size is 0.26.

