9.7. Data Analysis

Data will be analysed per arm. For categorical variables, numbers and percentages of patients will be reported including the according 95% confidence intervals.

For continuous variables, mean, standard deviation (SD), minimum, first and third quartile (Q1, Q3), median, and maximum will be calculated, together with the total number of observations and the number of missing values.

Missing values will not be imputed but classified as an own category to keep them for multivariate analyses.

Descriptive and multivariate data analysis will be done per treatment arm. Some cross arm comparisons according to sub groups (age \geq 50 years) might be conducted depending on group size.

Descriptive statistics will summarize demographics and baseline characteristics (including the type of regimen at enrollment).

The questionnaires scores will be calculated according to the algorithms elaborated for these questionnaires.

Visit windows will be defined (in the statistical analysis plan) to group data in order to generate descriptive statistics across time to assess potential trends in patient reported outcome questionnaires, safety data or CD4. P-values and/or confidence intervals (95% two-sided) will be calculated when considered relevant.

Multivariate analyses per arm (logistic regression) will be conducted to compare treatment naïve and non-naïve treatment groups adjusting for covariates. Longitudinal analysis will be done using mixed models.

Demographics and baseline measures would be potential confounders/effect modifiers for multivariate analyses. Confounders/effect modifiers and respective adjustments will be addressed in the Statistical Analysis Plan.

ADRs/SADRs and comorbidities will be coded using the Medical Dictionary for Regulatory Activities (MedDRA).

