1.1 Does the protocol specify timelines for				
1.1.1 Start of data collection ¹				16
1.1.2 End of data collection ²				16
1.1.3 Study progress report(s)				
1.1.4 Interim progress report(s)				
1.1.5 Registration in the EU PAS register				16
1.1.6 Final report of study results.				16

Comments:

--

Section 2: Research question	Yes	No	N/A	Page Number(s)
2.1 Does the formulation of the research question and objectives clearly explain:				
2.1.1 Why the study is conducted? (e.g. to address an important public health concern, a risk identified in the risk management plan, an emerging safety issue)				17, 18
2.1.2 The objective(s) of the study?				19
2.1.3 The target population? (i.e. population or subgroup to whom the study results are intended to be generalised)				20, 21
2.1.4 Which formal hypothesis(-es) is (are) to be tested?				
2.1.5 If applicable, that there is no a priori hypothesis?				

¹ Date from which information on the first study is first recorded in the study dataset or, in the case of secondary use of data, the date from which data extraction starts.

² Date from which the analytical dataset is completely available.

Comments:

No formal hypothesis testing, comparisons between various subgroups will be done using logistic or longitudinal models.

Section 3: Study design	Yes	No	N/A	Page Number(s)
3.1 Is the study design described? (e.g. cohort, case-control, randomised controlled trial, new or alternative design)				20

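### Section 9.5's 80% power at effect size 0.26 does not follow from 150 versus 150 subjects per arm: a plain two-sided 5% t-test has 61%, and the effect size is tied to no named outcome

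*Protocol*

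**What the plan says.** Protocol section 9.5 opens with a table of viral suppression percentages from earlier studies. It then states that the planned arm size of 300 "will provide 80% power to detect a difference in the treatment-naïve and treatment-experienced group means when the expected effect size is 0.26". For that calculation it gives no outcome, standard deviation, significance level, sidedness, model or allowance for missing data.

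The sizes of the compared groups are in section 9.2.2: "the study will enroll in each arm approximately 150 treatment-naïve and 150 treatment-experienced subjects". Section 9.1 and the synopsis give the same split. Section 9.7 sets out the comparison: "Multivariate analyses per arm (logistic regression) will be conducted to compare treatment naïve and non-naïve treatment groups adjusting for covariates". It adds that longitudinal analyses will use mixed models, and that confidence intervals, where given, are 95% two-sided.

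Two other places bear on how much weight the figure carries. Section 8 makes change in HIV-1 RNA and in CD4 cell count the primary objective. The comment to section 2 of the ENCePP checklist (Annex 2) reads "No formal hypothesis testing, comparisons between various subgroups will be done using logistic or longitudinal models".

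**The concern.** The power sentence concerns two groups inside an arm, but the number attached to it is the size of the whole arm. With 150 subjects on each side, 0.26 standard deviations looks too small a difference to be detected with 80% power.

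This is the protocol's only power statement. If it is carried into the report, a non-significant naïve versus experienced comparison could be taken to mean that a difference of 0.26 would have been missed only 20% of the time. Under a plain t-test it would be missed about 39% of the time. A reader also cannot tell whether 0.26 refers to CD4 change, a questionnaire score or something else.

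**Working it through.** **Inputs**
- Effect size d = 0.26, read as a difference in means divided by the common standard deviation (section 9.5).
- n = 150 per group (sections 9.1 and 9.2.2), compared within an arm (section 9.7).
- Two-sided α = 0.05. Section 9.5 states no level; this is taken from the 95% two-sided intervals in section 9.7.

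**1. Can the 80% be reproduced?**

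Normal approximation: power = Φ(d·√(n/2) − z), with d·√(n/2) = 0.26 × √75 = 2.252.

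- Two-sided 5%: Φ(2.252 − 1.960) = Φ(0.292) = 61.5%. The exact noncentral-t value is 61.2%.
- One-sided 5%, or two-sided 10%: Φ(2.252 − 1.645) = Φ(0.607) = 72.8% (72.6% by t for one-sided 5%).
- One-sided 10%: 83.4%.
- Two-sided 5% divided over three arms: 44.3%.
- Unequal splits of 300: all below 61.5%. For example, 200 versus 100 gives 56.5%.

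To reach 80% with 150 per group, z may be at most 2.252 − 0.842 = 1.410, which is a two-sided α of about 0.16. No conventional level comes within two points of 80%.

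**2. What would give 80%?**
- Required n per group at d = 0.26: 2 × ((1.960 + 0.842)/0.26)² = 232.2, so 233. The t-test needs 233.2, so 234 per group and 468 per arm.
- Detectable d with 150 per group: (1.960 + 0.842) × √(2/150) = 0.323. The t-test gives 0.325, which is 25% larger than 0.26 (0.325/0.26 = 1.25).
- With 300 in each compared group: 0.26 × √150 = 3.184, and Φ(3.184 − 1.960) = 89.0%. A loss of about 23% brings this down to 80% (232.2/300 = 0.774).

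**3. Missing data**

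Section 9.9 expects missing data of unpredictable extent and gives no rate. As an assumed range, again at two-sided 5% (normal approximation):

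| Missing | n per group | Power at 0.26 |
|---|---|---|
| 10% | 135 | 57% |
| 20% | 120 | 52% |
| 30% | 105 | 47% |

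**4. Do the suppression percentages yield 0.26?**

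The only naïve/experienced pair for the same drug and time is 92% and 97% (E/C/F/TAF, 48 weeks).
- Cohen's h = |2·arcsin√0.97 − 2·arcsin√0.92| = 0.225.
- Standardised difference = 0.05/√((0.97×0.03 + 0.92×0.08)/2) = 0.05/0.2266 = 0.221.

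Neither is 0.26. Pairs taken across drugs or time points do not give it either; the closest tried, 94% and 87%, has h = 0.243.

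**5. Could a more efficient analysis reach 80%?**

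The residual variance would have to fall to 150/232.2 = 0.646 of its unadjusted value.
- Baseline adjustment: 1 − r² = 0.646, so r ≈ 0.60.
- Mean of five follow-up measurements: (1 + 4ρ)/5 = 0.646, so ρ ≈ 0.56 or lower.

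**The case against.** The best defence is that section 9.5 names no test. The 61% assumes one unadjusted measurement per patient, whereas the protocol plans five follow-up visits, covariate adjustment and mixed models. A baseline correlation of about 0.60, or a correlation of about 0.56 among five follow-up values, would bring 150 versus 150 to 80%. This stands as a limit on the claim: one cannot say that no analysis of this design could reach 80%. It does not rescue the sentence, which speaks simply of group means and states no correlation or model.

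Three stronger readings are tempting, and the protocol supports none of them.
- A reader might infer that 0.26 was calculated from the suppression percentages. Section 9.5 never says so, and the same-drug pair gives about 0.22. The percentages are background.
- A reader might infer that a power for means is out of place because the naïve versus non-naïve comparison is by logistic regression. But CD4 change is a continuous part of the primary objective and mixed models are planned, so a mean comparison has a natural home. The defect is that the sentence does not name it.
- A reader might infer that 300 was mistakenly used as the size of each compared group. With about 23% loss that would reproduce 80%, but it is conjecture.

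It is also fair to say that little hangs on the figure. The objectives are descriptive, the checklist disclaims formal testing, section 9.2.2 gives subgroup evaluation as a separate reason for 300 per arm, and no decision rule uses the 80%.

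**Conclusion.** The point holds. The printed 80% cannot be reproduced from the protocol's own group sizes. At d = 0.26 with 150 versus 150, power is 61% by a two-sided 5% two-sample t-test and 73% by a one-sided 5% test. The difference detectable with 80% power is about 0.325.

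This rests on three assumptions: that 0.26 is a standardised mean difference, that the level and sidedness are those of section 9.7, and that each subject contributes one unadjusted value with nothing missing. Missing data would lower the figure. An efficient adjusted or repeated-measures analysis could raise it, by an amount the protocol gives no means of judging. The effect size also has no named outcome.

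This should be fixed, but it is not critical. The descriptive estimates and their confidence intervals are unaffected. What is wrong is the stated sensitivity of one comparison. A later analysis plan could not make the sentence true as printed.

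**What to change.** Replace the power sentence in section 9.5 with text such as:

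> With 150 treatment-naïve and 150 treatment-experienced subjects per arm, a two-sided 5% two-sample test of a continuous outcome (eg, CD4 cell count change) has 80% power for a standardised difference of 0.325 (61% for 0.26), before any loss to missing data.

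If the sponsor had an adjusted or repeated-measures analysis in mind, the sentence should instead state the outcome, the model and the assumed correlation, so that the 80% can be checked. Whichever version is adopted should be carried into the report.

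Optionally, add the precision for viral suppression, which suits a descriptive aim. At n = 150 the 95% half-width is 1.96 × √(0.92×0.08/150) = ±4.3 points at 92%, and 1.96 × √(0.97×0.03/150) = ±2.7 points at 97%.

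The cost is one paragraph in the protocol and the matching text in the report. No extra patients or data are needed. The downside is a less favourable stated figure.
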